## 13.2 Statistical Analysis

Twelve patients with CF will participate in this study. The endpoints for this study are descriptive in nature and the sample size is similar to other studies with these endpoints.

Patient demographics, clinical characteristics, and pharmacokinetic parameters will be summarized using descriptive statistics.

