
The pharmacokinetics of a number of medications have shown to be altered in patients with CF [11,12]. In general, patients with CF demonstrate an increased volume of distribution when expressed in L/Kg of body weight, and increased total body clearance. In addition, the oral bioavailability of lipophilic medications is reduced due to pancreatic insufficiency. To our knowledge no study has evaluated the pharmacokinetics of omadacycline in patients with CF. The proposed study is designed to characterize the pharmacokinetics of intravenous and oral omadacycline in patients with CF and determine the optimal dosing regimen in preparation for future efficacy and safety studies in CF patients with MABSC lung infections.

The pharmacokinetics of omadacycline in healthy volunteers, special populations, and patients with complicated skin and skin structure infections has been well described [7-9]. The oral absorption is relatively rapid and the bioavailability is good. Of note is the reduced bioavailability observed with high-fat meals or in conjunction with dairy products; based on these observations omadacycline is recommended to be given under fasting conditions with no food or dairy/antacids/multivitamins for 2 and 4 hours after administration respectively [10]. Elimination of omadacycline occurs predominately through fecal excretion [10]. No dosage adjustment is necessary for renal or hepatic disease [10].

Of particular importance to the proposed study is the excellent pulmonary penetration of omadacycline noted in healthy volunteers [9]. Bronchoalveolar lavage studies performed at

steady-state following omadacycline 100mg IV daily revealed epithelial lining fluid and alveolar macrophage exposures 2-fold and 30-fold higher respectively, than free drug exposures in plasma. These exposures also exceeded that of tigecycline indicating greater pulmonary penetration with omadacycline.

Our study hypothesis is that omadacycline will exhibit good oral bioavailability in patients with CF.

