### 10.2 Endpoint Definitions

PK parameters of omadacycline including the area under the curve, maximum concentration and time to maximum concentration in patients with CF.

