## 13.0 DATA/STATISTICAL CONSIDERATIONS

### 13.1 Pharmacokinetic analysis

Pharmacokinetics will be performed using standard noncompartmental methods.

The maximum concentration and time to maximum concentration will be from the

observed data. The area under the curve will be calculated using the trapezoidal rule. Absolute bioavailability will be determined by a ratio of the  $AUC_{PO}/AUC_{IV}$ .

In addition, population pharmacokinetic analysis will be performed using the maximum likelihood estimation via the EM algorithm with sampling (MLEM) as implemented in ADAPT 5 (Biomedical Simulations Resource, University of Southern California). Multiple candidate models will be evaluated to identify the model that best describes the observed plasma concentration data.

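### Absolute bioavailability is defined without a dose term although the IV and oral doses differ threefold, and the plan does not say how the individual ratios are formed or summarised

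*Combined protocol and SAP*

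**What the plan says.** Sections 3.0 and 7.1 give every patient one 100 mg IV dose and, after a week's washout, one 300 mg oral dose. Section 13.1 then says: "Absolute bioavailability will be determined by a ratio of the" oral AUC to the intravenous AUC. The expression printed there is AUC_PO/AUC_IV. It contains no dose, and the text does not say whether the ratio is taken within each patient or between group averages.

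On summaries, section 13.2 puts the PK results in the same sentence as demographics and clinical characteristics: "pharmacokinetic parameters will be summarized using descriptive statistics". No type of mean, scale, measure of spread or interval is named. The same section states "The endpoints for this study are descriptive in nature" and justifies the 12 patients on the ground that "the sample size is similar to other studies with these endpoints".

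Section 10.2 lists the endpoints as "PK parameters of omadacycline including the area under the curve, maximum concentration and time to maximum concentration in patients with CF". Bioavailability is not named there, yet it is the subject of the one stated hypothesis, in section 1.0: "Our study hypothesis is that omadacycline will exhibit good oral bioavailability in patients with CF". No value is given for what counts as good.

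**The concern.** There are two gaps, of very different size.

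The first is in a stated rule. A ratio of AUCs equals absolute bioavailability only when the doses are equal or each AUC is divided by its dose. Here the doses differ threefold, so the printed formula does not return the quantity it is said to define.

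The second is in what is left unsaid. F is a ratio of two AUCs, each measured with error in the same patient. The mean of such ratios on the raw scale tends to lie above the underlying value, because error in a denominator does not average out as error in a numerator does. A geometric mean largely avoids this. The plan leaves open which is used, and whether the ratio is formed per patient at all. The latter matters if someone leaves after the IV dose, since a ratio of group averages would then compare different sets of patients.

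At stake is the number that readers will compare with the hypothesis. Section 1.0 also says the study is meant to inform dosing for later trials, so F has a use beyond this report.

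**Working it through.** **Plan's own figure.** There is none to reproduce. The documents give no expected F and no CV, and the sample size of 12 rests on precedent alone.

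**Dose term.** Inputs: 100 mg IV and 300 mg oral (sections 3.0 and 7.1). Assumption: linear kinetics with the same clearance CL on both occasions.

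- AUC_IV = 100/CL and AUC_PO = F × 300/CL.
- AUC_PO/AUC_IV = F × 300/100 = 3F.

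For assumed true F of 0.20, 0.35, 0.50 and 0.80, the printed formula returns 0.60, 1.05, 1.50 and 2.40. A result above 1 would show that something is wrong. When F is below 1/3, the result stays below 1 and looks plausible.

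**Averaging scale.** Assumptions: log-normal AUC errors and the same within-patient CV on both routes. The CV is not in the documents, so 10% to 30% is an assumed range. Write s² = ln(1+CV²) and let ρ be the correlation between the two errors on the log scale. The log ratio then has error variance 2s²(1−ρ), and the expected raw-scale ratio exceeds the target by exp{s²(1−ρ)}. That is 1+CV² for independent errors (ρ = 0) and √(1+CV²) for ρ = 0.5.

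For scale, the table also gives the 95% sampling factor for a geometric mean of 12 ratios with independent errors, exp{t × √2 × s/√12}, where t = 2.201 on 11 degrees of freedom.

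| Assumed within-patient CV | s | Inflation, ρ = 0 | Inflation, ρ = 0.5 | 95% factor, n = 12 |
|---|---|---|---|---|
| 10% | 0.0998 | 1.010 | 1.005 | 1.09 |
| 20% | 0.1980 | 1.040 | 1.020 | 1.19 |
| 30% | 0.2936 | 1.090 | 1.044 | 1.30 |

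Example at 30%: 1 + 0.09 = 1.09; √1.09 = 1.044; exp(2.201 × 1.4142 × 0.2936/3.4641) = exp(0.264) = 1.30.

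The sampling factor counts within-patient error only; real variation in F between patients would widen it. The geometric mean of 12 ratios is not exactly free of shift either. Its expectation is above the true geometric mean by (1+CV²)^(1/12), which at 30% is 1.09^(1/12) = 1.007.

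**The case against.** On the dose term, the best defence is that section 13.1 invokes standard noncompartmental methods, and an experienced analyst divides by dose as a matter of course. The population model would also normally take the doses as inputs. A reader might infer that the trial will report a bioavailability three times too high. The documents do not support that: they show only that the formula, applied as printed, would do so. What stands is that an explicit formula is given and it is incomplete, and nothing elsewhere in the plan supplies the missing term.

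On averaging, a reader might infer that the plan builds in a bias toward its hypothesis. It does not, for four reasons:

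- Descriptive statistics can mean medians or geometric means as well as arithmetic means, and nothing commits the analysis to a raw-scale mean of ratios.
- Whether a raw-scale mean overstates F depends on the target. If F truly differs between patients and the average F is wanted, that part of the gap between arithmetic and geometric means is not bias. Only within-patient AUC error then inflates the result.
- The inflation shrinks when the two AUC errors are positively correlated, and every CV used here is assumed.
- No threshold for good bioavailability, no test and no interval is planned, so no decision is shown to change and there is no planned interval whose coverage could be criticised.

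All four reasons stand. They reduce the averaging point to a choice that should be fixed in advance. They do not touch the dose term.

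**Conclusion.** The concern holds in two parts. The definition of absolute bioavailability in section 13.1 omits the dose and, read literally, gives 3F under linear kinetics with equal clearance on both occasions. This is the larger part, and it corrects a rule the plan states.

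The unstated summary method is the smaller part. A raw-scale mean of individual ratios would be expected to run high by about 1%, 4% or 9% at assumed within-patient CVs of 10%, 20% or 30% with independent log-normal errors, and by less with positive correlation. At each of these CVs the shift is well inside the sampling error for 12 patients. It is a possible consequence of leaving the choice open, not an error the plan makes.

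**What to change.** - **Section 13.1:** state that F = (AUC_PO/300 mg)/(AUC_IV/100 mg), computed for each patient.
- **Section 13.2:** state that F, AUC and Cmax are summarised by geometric mean and geometric CV from the log scale, and Tmax by median and range. Arithmetic means may be shown as secondary.

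With complete pairs, the geometric mean of the individual ratios equals the ratio of the geometric means, so this also removes any ambiguity about how the group value is formed.

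The cost is one or two sentences, with no added patients, samples or visits. The one downside is that the headline F may be a few percent lower than a raw-scale mean of the same ratios.

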## 14.0 REGISTRATION GUIDELINE

14.1 Subjects will be registered into the study through submission of the research order form, informed consent, and patient bill of rights to the Clinical Trials Office (CTO) at USC.

## 15.0 BIOHAZARD CONTAINMENT

Not applicable

## 16.0 ETHICAL AND REGULATORY CONSIDERATIONS

All institutional and Federal regulations concerning the Informed Consent form will be fulfilled. The study will be conducted in adherence to ICH Good Clinical Practice.

